4. ESTIMATED DURATION OF THE STUDY

Each participant will be on PrEP with medication adherence support for 48 weeks after enrollment with a post-study follow-up at 60 weeks. The primary endpoint will be measured at 48 weeks. This will be a 4-year study.

Participants taking part in the extension will continue to receive PrEP at Week 48 and every 12 weeks thereafter up to 24 weeks until approval of CCTG 605 (HRPP# 191001) or FDA approval of emtricitabine/tenofovir alafenamide (F/TAF) for use as PrEP.

5. LAY LANGUAGE SUMMARY OR SYNOPSIS (no more than one paragraph)

The purpose of this study is to evaluate and compare adherence to Pre-Exposure Prophylaxis (PrEP) in transgender-identifying or gender non-conforming individuals who receive daily, text message-based medication adherence reminders (iTAB) with vs. without brief Motivational Interviewing. This study will enroll 300 individuals (up to 100 at UCSD) to take PrEP for 48 weeks.

6. SPECIFIC AIMS

Study Primary Objective: To compare adherence to fixed dose TDF/FTC, as measured by intracellular levels of TFV-DP \geq 1246 fmol/punch, between subjects randomized to receive iTAB with versus without brief Motivational Interviewing, when used for adherence support to pre-exposure prophylaxis among transgender / gender non-conforming (TG / GNC) individuals at elevated risk for HIV acquisition.

Hypothesis: Subjects randomized to the iTAB intervention plus MI-b will have higher adherence, as measured by intracellular levels of TFV-DP ≥ 1246 fmol/punch, at both week 12 and their last visit after week 12 up until 48 weeks (eg week 24, 36 or 48), compared to those with iTAB alone in those that complete those visits and have a measureable level. To be considered adherent they must have attended the week 12 visit; if week 12 was attended but was the last visit, then only the week 12 visit will be required for the endpoint.

Study Secondary Objectives

To compare adherence to fixed dose TDF/FTC, as measured by intracellular levels of TFV-DP ≥ 719 fmol/punch, between subjects randomized to receive iTAB with versus without brief Motivational Interviewing, when used for adherence support to pre-exposure prophylaxis among transgender / gender non-conforming individuals at elevated risk for HIV acquisition.

Hypothesis: Subjects randomized to the iTAB intervention plus MI-b will have higher adherence as measured by intracellular levels of TFV-DP \geq 719 fmol/punch, at both week 12 and their last visit after week 12 up until 48 weeks (eg week 24, 36 or 48), compared to those with iTAB alone in those that complete those visits and have a measureable level. To be considered adherent they must have attended week 12 visit; if week 12 was attended but was the last visit then only the week 12 visit will be required for the endpoint.

- 2. To compare adherence to TDF/FTC in the iTAB+MI-b versus iTAB alone arms using
 - a) a continuous outcome of DBS TFV-DP drug levels at weeks 12 and 48 in participants who attended both visits
 - b) TFV-DP intracellular levels of ≥ 1246 fmol/punch and ≥ 719 fmol/punch at both week 12 and week 48
 - c) a stratified analysis of drug level outcomes within male-assigned at birth and female-assigned at birth groups
 - d) a composite endpoint with the outcome defined as "all attended visits (regardless if they missed week 12)" with levels of \geq 1246 fmol/punch and \geq 719 fmol/punch.
- 3. To compare self-reported adherence to TDF/FTC in the iTAB+MI-B versus iTAB arms over 48 weeks using
 - a) adherence defined as "the proportion of text-reported doses over all possible doses over 48 weeks"; missing text messages or early discontinuation of the study will be considered as no doses taken
 - b) a continuous measure of the percentage of days adherent by self reported measures (iTAB, cumulative 3 day recall, and the visual analog scale) in an "as treated" analysis for those that are retained on study
- c) stratified analysis of 3a and 3b outcomes within male-assigned at birth and female-assigned at birth groups
- 4. To compare study retention between arms, defined as the proportion of participants that complete all study visits regardless of whether they were on drug or not
- 5. To determine factors associated with poor adherence (< 719 fmol/punch over 48 weeks) and discontinuation of TDF/FTC
 - Factors considered to be associated with poor adherence to TDF/FTC will include demographics, socioeconomic status, perception of HIV risk, ongoing substance use, intimate partner violence, low health/HIV and health systems literacy, and stigma
- 6. To determine the rate of linkage and continuation of TDF/FTC at 12 weeks after study completion between arms
- 7. To determine the rate of HIV seroconversion in TDF/FTC-using transgender / gender non-confirming individuals and compare the proportion of seroconversions over 48 weeks between arms
- 8. To measure the acquisition of other sexually transmitted infections (STIs) and compare rates of acquisition of new STIs at any site between arms
- 9. To evaluate changes in risk behavior after PrEP initiation (risk compensation) by comparing the numbers of HIV positive partners, partners of unknown HIV status, unprotected insertive and receptive anal or vaginal acts between Baseline and subsequent visits
- 10. To evaluate the safety and tolerability of daily TDF/FTC as PrEP as measured by discontinuations due to
 - a) any adverse events
 - b) serious adverse events and
 - c) grade 2 or higher adverse events

Sub-study I Primary Objective: To determine whether csHT interacts with PrEP in male-assigned at birth (MAAB) persons that would affect efficacy of PrEP, measured by intracellular TDF concentrations in DBS.

Hypothesis: Among transgender MAAB persons on csHT who report perfect adherence by iTAB in the past 34 days (ie, two intracellular half-lives) the mean intracellular tenofovir-diphosphate (TFV-DP) concentrations, as measured in DBS, will be equivalent to the levels of perfect adherence previously defined in MSM.

Sub-study I Secondary Objectives

- 1. To determine whether csHT interacts with PrEP in MAAB persons that would affect hormone effectiveness, measured by estrogen concentrations assessed at Weeks 0 and 12 of study follow-up.
 - **Hypothesis**: Among transgender MAAB persons on csHT, estrogen concentrations will not change significantly between baseline (Week 0) and Week 12 in individuals taking PrEP and receiving stable estrogen therapy (controlling for route and formulation).
- 2. To determine TFV-DP in MAAB of all adherence levels compared to not taking csHT, adjusting for confounding factors.
- 3. To determine TFV-DP in MAAB taking versus not taking antiandrogen medications (i.e., spironolactone, finasteride)
- 4. To measure the change in testosterone concentrations between baseline and Week 12 in female-assigned at birth (FAAB) taking PrEP and receiving stable testosterone therapy.
- 5. To determine emtricitabine-triphosphate (FTC-TP) concentrations (a measure of recent adherence) in TG / GNC persons of all adherence levels taking versus not taking hormones.
- 6. To determine changes in desired effects of csHT in TG / GNC persons taking PrEP as measured by the Body Image Scale (BIS).

Sub-study IV Objectives:

- 1. To determine the impact of genital STIs on CVF TFV levels.
- 2. To determine the impact of cytokine mediators of CV inflammation on CVF TFV levels.
- 3. To determine the impact of CV microbiome on CVF TFV levels.

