For security measures, the database is password protected, fully encrypted and only accessible by the Data Manager. Data management for this study will be provided through the Open Source Clinical Content Management System (OCCAMS) developed by the CCTG Data Core. OCCAMS provides integrated, flexible, and secure tools for complex clinical study data management using only a web browser. The Data Core ensures data security though a robust security model consisting of a multi-level hardware/software firewalled network, secure hardware and software encryption, data auditing and access tracking procedures, and completely redundant services hosted from two physically separated server facilities. Therefore the input and extraction of this data is only done by personnel with appropriate access to the system. Study personnel will use OCCAMS from a web browser to manage all data storage, quality control, and retrieval. Each staff member will be provided a login and password and will be assigned to the appropriate role-based groups using the UCSD campus active directory. Membership in these role-based groups will provide users with the necessary web views to complete their assigned tasks on a need to know basis. Information from the database will only be shared with the research team. The research team includes the researchers and people hired by the University or an outside company who contracts with the University to sponsor the research activities being done at the AVRC.

STATISTICAL CONSIDERATIONS

A formal Statistical Analysis Plan (SAP) will be drafted and finalized prior to database lock. The SAP will contain a more detailed and/or comprehensive presentation of statistical methods; attention to any changes of substance to planned analysis procedures relative to those indicated in the protocol will be submitted as an amendment. The SAP is the final authority for all statistical analyses. The following section briefly describes the planned statistical analyses. In case the language in this section differs from the language in the SAP, the SAP takes precedence.

Primary Endpoints

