The primary endpoint will be a composite adherence outcome determined by dried blood spot intracellular tenofovir diphosphate (TFV-DP) levels. A subject will be considered adherent if the TFV-DP levels are above 1246 fmol/punch (consistent with 7 doses in past week) at both week 12 and the last study visit over the 48 weeks. All randomized subjects that were dispensed PrEP at baseline will be included in the modified intent-to-treat analysis. Participants not achieving week 12 will be considered non-adherent.

Secondary Adherence Endpoints

A key secondary endpoint will be a composite outcome determined by TFV-DP levels at both week 12 and the last study visit associated with adequate adherence (>719 fmol/punch).

Self-reported adherence to PrEP through 48 weeks is defined as the proportion of text-reported doses over all possible doses in 48 weeks. Missing responses due to either missed text messages or early discontinuation of the study will be considered as no doses taken. Sensitivity analysis will also be done on the 'as-treated' population (i.e. treat missing as missing).

Additional self-reported adherence measure will be >90% adherence (i.e. on the ACTG 4-day recall at weeks 12, 24, 36, and 48); >90% dosing by VAS at each study visit.

- Poor adherence is defined as < 4 doses a week or discontinuation of study drugs. Subgroup analysis will explore the endpoint for discontinuation for reasons other than lack of risk or confirmed adverse event.
- Safety and tolerability outcomes are defined as incidence rates of: i) discontinuation of TDF/ FTC for any toxicity; ii) grade 2 or higher adverse event (symptoms or laboratory toxicity); iii) serious adverse events; iv) death

Randomization and Stratification

Subjects will be randomized (1:1) to one of two arms: the **iTAB** or the **iTAB+MI-B** enhanced adherence arm. Randomization will be stratified by clinic site, sex assigned at birth (male vs female), and prior history of PrEP use. Participants assigned "intersex" at birth will be included in the female group. A total of 300 subjects (150 per arm) will be randomized and followed in the study for 48 weeks after enrollment of the last subject.

Once eligibility and consent are confirmed, randomization will occur using the web-based CCTG data management system.

Study Power and Sample Size Justification

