The study is powered to compare the primary adherence rate between the two study arms using a two-sample, two-sided proportion test. Expected drug-level adherence based on a previous study of MSM using iTAB for PrEP for this composite endpoint (>=1246) was 33%. Assuming the adherence rate of the transgender iTAB alone group will be the same the study has 77% power to detect a difference of 16% between the iTAB+MI group and the iTAB alone group, with 150 subjects per group.

Monitoring

The study team will review all adverse events during PrEP therapy as cumulative reports in both arms combined, on monthly team calls. Adverse events will be graded using the ACTG toxicity grading scale and recorded using standard CCTG AE electronic data capture. An independent Data Safety and Monitoring Board (DSMB) will not be used for this study because the drugs are licensed for this indication and relatively non-toxic.

Statistical Analysis Plan

In general, analyses of efficacy will incorporate the modified intent-to-treat (mITT) principle, namely, all randomized participants dispensed study medication will be included in the analysis. For all secondary analyses of efficacy, no adjustments for multiple comparisons will be made and a p-value of 0.05 will be considered statistically significant. Analyses of safety will be focused on "as treated" populations.

Demographic and baseline measurement variables will be summarized via standard descriptive statistics. There will be no interim analyses for futility or efficacy conducted.

Analysis of Primary Outcome

Descriptive analysis will be performed on the primary adherence outcome via a frequency table and Fisher's exact test. Logistic regression modeling will be conducted to assess the group differences while adjusting for potential covariates.

Analysis of additional Secondary outcomes

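### The primary and key secondary hypotheses are confined to participants with a measurable drug level, which contradicts the plan's modified intent-to-treat population and conditions on behaviour after randomization

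*Combined protocol and SAP*

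**What the plan says.** Section 6 (Specific Aims) gives the hypothesis for the primary endpoint, and in the same terms for the 719 endpoint, as a comparison of iTAB plus MI-b "compared to those with iTAB alone in those that complete those visits and have a measureable level". The next sentence of the primary hypothesis reads "To be considered adherent they must have attended the week 12 visit", and it goes on: "if week 12 was attended but was the last visit, then only the week 12 visit will be required for the endpoint".

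Section 9, Primary Endpoints, defines success on the same composite: "A subject will be considered adherent if the TFV-DP levels are above 1246 fmol/punch" at week 12 and at the last study visit. It then sets the population, "All randomized subjects that were dispensed PrEP at baseline will be included in the modified intent-to-treat analysis", and one missing-data rule, "Participants not achieving week 12 will be considered non-adherent". The Statistical Analysis Plan paragraph of section 9 extends this to efficacy analyses in general, hence to the 719 endpoint: "all randomized participants dispensed study medication will be included in the analysis".

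Three operational rules in section 9 bear on who has a level. At in-clinic visits the dried blood spot (DBS) is taken from participants on PrEP. The schedule for participants on study but off medication keeps the visits and omits the DBS. Footnote 2 to the Schedule of Evaluations lets participants restart PrEP up to the end of the week 36 visit.

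On precedence, section 9 says of a document still to be drafted: "The SAP is the final authority for all statistical analyses".

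**The concern.** The two sections give different denominators for the same two endpoints. Section 6 is also at odds with itself: someone who misses week 12 is excluded by the restriction, yet cannot be adherent under the next sentence.

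The difference matters because having a level requires attending and being on PrEP, which are part of what the intervention is meant to change. A participant can attend week 12 off PrEP, have no DBS by design, restart, and have a level later. The section 6 restriction removes that person; section 9 keeps them in the denominator. If such cases differ by arm, the restricted comparison shifts toward the arm with more of them. It could produce a false benefit if MI-b has more missing levels, or hide part of a real one if MI-b keeps more people on PrEP.

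Two details are unstated: how an attended visit without a level is scored, and whether measurable means a result is available or that it is above the limit of quantification.

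**Working it through.** **Inputs from the documents.** 150 per arm, 33% control adherence, a 16-point difference (33% vs 49%), a two-sided test, and Fisher's exact test for the primary outcome (section 9). Alpha 0.05 is stated for the secondary analyses and assumed here for the primary.

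**Assumed inputs.** m is the share of an arm without a level; s is the share of those people who are truly adherent. The documents give neither. Dropout after week 12 does not by itself count toward m, because the last attended visit then serves. The relevant cases are a missed week 12, or an attended week 12 or last visit without a DBS.

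**The plan's own figure.** Continuity-corrected normal power = Φ[(Δ − 1/n − 1.96·SE0)/SE1], with
- SE0 = √(2 × 0.41 × 0.59/150) = 0.0568
- SE1 = √(0.33 × 0.67/150 + 0.49 × 0.51/150) = 0.0560

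This gives (0.16 − 0.0067 − 0.1113)/0.0560 = 0.75, so power is 77.3%. Exact Fisher power is 78.1%. The stated 77% therefore reproduces with all 150 per arm, which fits the section 9 population.

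**Formulas, with p the true rate over everyone dispensed PrEP.**
- Section 6 restriction: rate (p − m·s)/(1 − m) on about 150(1 − m) people.
- No level scored as failure: rate p − m·s on 150 people.

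**No true difference, p = 0.33 in both arms, s = 0.** Missing-as-failure gives 33% vs 33% and rejects in 3.75% of trials, whatever m is. Under the restriction:

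| Missing (arm 1 vs arm 2) | n | Rates compared | Rejection rate |
|---|---|---|---|
| 5% vs 10% | 143 vs 135 | 34.7% vs 36.7% | 5.5% |
| 10% vs 20% | 135 vs 120 | 36.7% vs 41.3% | 10.0% |
| 20% vs 30% | 120 vs 105 | 41.3% vs 47.1% | 13.1% |
| 10% vs 10% | 135 vs 135 | 36.7% vs 36.7% | 3.8% |
| 20% vs 20% | 120 vs 120 | 41.3% vs 41.3% | 3.8% |

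At 10% vs 20%, 9.75% of trials falsely favour the arm with more missing levels and 0.27% the other arm. At 20% vs 30% the split is 12.90% and 0.18%.

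**No true difference, s = 0.2.** Missing-as-failure can no longer recover the true rate either.
- 10% vs 20% missing: the restriction compares 34.4% with 36.3% and rejects in 5.25%. Missing-as-failure compares 0.33 − 0.02 = 31% with 0.33 − 0.04 = 29% and rejects in 5.15%.
- 20% vs 30% missing: the restriction compares 36.3% with 38.6% (5.31%). Missing-as-failure compares 29% with 27% (5.18%).

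The restriction leans toward the arm with more missing levels, missing-as-failure toward the arm with fewer.

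**True effect 33% vs 49%, with 20% missing on iTAB alone and 10% on MI-b.**
- s = 0: the restriction gives 0.33/0.80 = 41.3% vs 0.49/0.90 = 54.4%, 13.2 points, power 54.1%. Missing-as-failure gives the true 16 points, power 78.1%.
- s = 0.2: the restriction gives 0.29/0.80 = 36.3% vs 0.47/0.90 = 52.2%, about 16 points, power 71.2%. Missing-as-failure gives 29% vs 47%, 18 points against a true 16, power 87.6%.

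**The case against.** The strongest reply is that the statistics section already settles the matter. With everyone dispensed PrEP in the denominator and adherence requiring levels above the cut-off at both visits, an attended visit without a level cannot succeed. Section 6 is only a hypothesis statement, and a later SAP can supply the detail. The deduction is sound, but it remains a deduction. The precedence rule places the SAP above the statistics section; it does not place that section above the Aims. A SAP author could follow either text.

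A second reply is that the larger error rates depend on the assumptions. This stands. They need a sizeable imbalance in missing levels, no difference in overall adherence, and nobody without a level being adherent. At 10% vs 13% missing with s = 0, the error is 4.6%.

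A third is that missing-as-failure is not an unbiased reference. This also stands when some of those without a level are adherent, as the s = 0.2 results show.

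A reader might also infer that the week-12-only rule is missing from section 9. It is not: if week 12 is the last visit, the two required visits coincide. Nor is a stricter analysis absent, since secondary objective 2b already uses week 12 and week 48. One might further suspect the 33% planning rate, but its denominator is a separate planning question that these documents cannot settle.

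**Conclusion.** The contradiction is real and affects both the primary and the key secondary endpoint. Following section 6 would condition the comparison on attendance and on staying on PrEP. The advantage of section 9's population is clear mainly for participants who have no level because they are off PrEP, where assuming s near 0 is reasonable; there the null error could rise from 3.75% to between 5.5% and 13.1% under the assumed imbalances. For people still on PrEP with an undrawn sample or failed assay, neither approach is clearly better.

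A reader might infer that the plan has no intent-to-treat analysis, or that the trial's false-positive rate is 10% or more. The documents support neither. The modified intent-to-treat population and the week 12 failure rule are explicit, the stated power fits that population, and the error rates are illustrations. With equal missingness in the two arms there is no bias in the null illustration. This should be fixed before the SAP is finalized.

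**What to change.** 1. In section 6, delete the restriction to completers with a measurable level from both hypotheses, and state the modified intent-to-treat population there.
2. In section 9, Primary Endpoints and Secondary Adherence Endpoints, state for both thresholds that a participant is non-adherent if week 12 or the last attended visit has no level because they are off PrEP, or if the level is below quantification. For a participant on PrEP with an undrawn sample or failed assay, score non-adherent in the primary analysis and add a sensitivity analysis that treats the result as missing.
3. Report the measured-level comparison only as a sensitivity analysis, with counts and reasons for missing levels by arm. Carry the same wording into the SAP.

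The cost is wording; no new data are needed, since visits and PrEP use are already followed. The drawback is that participants on PrEP with an undrawn or failed sample are scored conservatively, which can bias the result toward the arm with fewer missing levels. The sensitivity analysis in item 2 addresses that.

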For participants with disqualifying safety laboratory results, the study coordinator will instruct the participant to immediately cease study medication and an interim screen failure visit will be scheduled at the clinic. The following procedures will be conducted at the screen failure visit:

- Participant will return any remaining study medications.
- Participants with disqualifying creatinine or creatinine clearance values may request to re-screen into the study but may not repeat a same-day PrEP initiation visit.
- If HBsAg positive, the participant will be referred to care.
- If HIV positive, study coordinators will follow the procedures outlined in 6.11.4 and 6.11.5 in the Protocol.
- Participant will be terminated from the study as a Screen Failure.

In-Clinic Study Visits (Weeks 12, 24, 36, and 48; approximately 1 hour)

Participants will be asked to return to the clinic at week 12 and every 12 weeks up to week 48. Study visit procedures include:

- Assessment of adverse events since last contact.
- Targeted medical history and physical examination, including collecting weight
- Review of concomitant medications, including detailed csHT use
- Laboratory evaluations
 - Rapid HIV screening
 - 3-site (throat, rectal, urine) STI NAAT screening for gonorrhea and chlamydia (weeks 24 and 48 only)
 - Syphilis RPR (weeks 24 and 48 only)
 - Calculated creatinine clearance (Cockcroft-Gault)
 - Plasma hormone levels for participants on csHT (week 12 only, sub-study only)
 - Urine β-HCG for participants capable of being pregnant.
- Sample collection for banking
 - Dried blood spot (DBS) for participants on PrEP
 - Whole blood, plasma, and serum
 - Urine
 - Rectal swabs (week 48 only)
- CASI assessments
- Medication dispensation. Participants will be provided enough medication to last until the next scheduled visit through the investigational pharmacy. Participants will not be provided PrEP at week 48.
- Risk reduction and medication adherence counseling. Counseling will not be performed at week 48.
- End of Study assessment (week 48 only). This survey will assess participant's experiences over the course of the study, including changes in their medical insurance status, access to other healthcare services, changes in perceptions of PrEP and of their own health, and their opinions about the intervention.

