- Ability to access and maintain their PrEP regimen since EOS
- Ability to access health insurance coverage since EOS
- If participant has not accessed PrEP and/or does not have health insurance, the participant will be asked for their reasons and possible barriers to uptake
- Adherence (if on PrEP)
- HIV risk behavior
- Perceptions of PrEP efficacy

Schedule of Evaluations for Subjects On-study, Off-medications

At any point of the study, participants may elect to stop study medication but remain on study. Participants not on study medication will follow the same schedule as defined in the schedule of evaluations until the end of study, with the following exceptions:

- Medication will not be dispensed
- Adherence counseling and monitoring of medications will not be performed
- DBS will not be collected
- iTAB account for participant will be switched to "inactive"

		Study Weeks of Follow-up								Interim ⁷	
Schedule of Evaluations	Screen	Wk 0	Same-day PrEP	2	12, 24, 36	48 / EOS	48 EXT ◊	60	Visit	Phone	
Window		30 days		+/- 1 week	+/- 4 weeks			+/- 4 weeks			
Informed Consent	Χ		Х								
Inclusion / Exclusion	Χ		Х								
Randomization		Χ	Х								
iTAB setup		Χ	X								

Medical/medication										1
history and targeted	Χ	Х	X		X	X	X		Χ	
physical exam										
HIV risk reduction		X	Х		Х		X			
counseling										
Adherence counseling ¹		Χ	X		X		Х			
TFV/FTC dispensed ¹		X	Χ		Х		Х		(X)	
Telephone follow-up				Χ				X		Χ
Adverse events				Х	Х	Х			(X)	(X)
assessment ¹				,,	^	^			(71)	(71)
Computer assisted self-	Х	Х	X		Х	Х				
interview (CASI) surveys	,,	,								
End of Study survey						Х				
Post-study survey						 		Χ		
Laboratory										
HIV EIA / NAT or Ag/Ab	Х		Х		(X) ²		(X) ²		(X) ²	
test					(^)		(^)		(^)	
HBsAg	Χ		X							
Creatinine and GFR	Х		X		Х	X	X			
(calculated CrCl) ¹					^	^	^			
Urinalysis	X		X							
Urine β-HCG ³	X	Χ	Х		X	X			(X)	
CBC, liver enzymes		Х	Х							
Rapid HIV		Х	Х		X	X	X		(X)	
STI screen [†] : GC, CT,		X	Х		X ⁵	X			(X)	
syphilis		^	^		Λ	^			` ,	
GC Treatment [†]									(X)	
Plasma hormone levels ⁴		Χ	Х		(X)					
Dried Blood Spot (DBS) ¹		(X) ⁶	(X) ⁶		X	X			(X)	
Banked whole blood,		Х	Х		Х	Х				1
serum, plasma										
Banked urine		Χ	X		X	X				
Banked rectal swabs		Х	Х			Х				
(x2)		^	^			^				
HIV confirmatory test if	(X)		Х		(X)	(X)	(X)	(X)	(X)	
HIV+	(//)				(//)	(//)	(//)	(//)	(//)	
CD4, HIV RNA, and HIV										
genotype if HIV+ after			Χ		(X)	(X)	(X)	(X)	(X)	
baseline										

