Descriptive analysis will be performed for all the secondary outcomes. For comparisons between the two study arms, Fisher's exact test will be used for categorical outcomes; t-test or Wilcoxon rank sum test will be used for continuous outcomes. Multivariable logistic regression model will be used to study factors associated with poor adherence. Factors will include demographics, substance use, untreated mental illness, socieconomic status, low health/HIV and system literacy, fear of disclosure and non-English language. To evaluate changes in risk behavior after initiation of PrEP, descriptive summary will be provided for the number of HIV positive/unknown status partners and any unprotected anal intercourse with an HIV positive/unknown status partner by visit (at w12, 24, 36 and 48). Wilcoxon signed rank test will be used for comparison at each follow-up visit to the baseline visit. GEE model will be used to assess the change in risk behavior over time.

Safety analysis

Safety data will be reported for all the randomized subjects while they were taking or immediately (30 days) after taking study drug (as treated analysis). Tables will summarize the number of serious adverse events, adverse events (grade 2 or higher), PrEP discontinuation due to adverse events, by study arms and overall. Fisher's exact test will be used to compare the rates between the two groups. The time to TDF/FTC discontinuation due to adverse events will be compared between groups using the log-rank test and plotted using Kaplan-Meier curves.

SUB-STUDY I DESIGN

This pharmacologic sub-study will use the main study cohort to determine the interaction of cross-sex hormone therapy (csHT) on PrEP efficacy as measured by TFV-DP and FTC-TP DBS intracellular levels, and of PrEP on csHT effectiveness as measured by quantitative hormone levels in plasma.

SUB-STUDY I PROCEDURES

Subjects will be consented for participation in the sub-study at the main study's Screening Visit.

As part of the main study, plasma and DBS samples will be collected at Baseline and every 12 weeks. A Baseline DBS sample will be collected only if the subject is already on PrEP at the time of Baseline. Detailed concomitant hormone use, including route and frequency, will be collected at every clinic visit. Daily iTab responses will be used as a self-reported adherence measure.

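### The continuous TFV-DP comparison (secondary objective 2a) is restricted to participants who attended both weeks 12 and 48, a subset formed after randomization that leaves out levels already collected

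*Combined protocol and SAP*

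**What the plan says.** Secondary objective 2a (section 6, Specific Aims) defines the outcome and its population together: "a continuous outcome of DBS TFV-DP drug levels at weeks 12 and 48 in participants who attended both visits".

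Section 9 supplies the rest:

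- Visits (In-Clinic Study Visits): "Participants will be asked to return to the clinic at week 12 and every 12 weeks up to week 48". The samples listed for each of these visits include "Dried blood spot (DBS) for participants on PrEP".
- Participants who stay on study but stop the drug keep the same schedule, except that, among other things, "DBS will not be collected".
- Efficacy population (Statistical Analysis Plan): mITT in general, so that "all randomized participants dispensed study medication will be included in the analysis".
- Method for continuous secondary outcomes: "t-test or Wilcoxon rank sum test will be used for continuous outcomes". No repeated-measures model, missing-data method or sensitivity analysis is given for the continuous level. The one missing-as-missing sensitivity analysis concerns text-reported doses.
- Secondary testing: "no adjustments for multiple comparisons will be made and a p-value of 0.05 will be considered statistically significant".
- Primary endpoint, by contrast: "Participants not achieving week 12 will be considered non-adherent", so those people remain in the analysis.

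Secondary objective 4 compares retention between the arms.

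**The concern.** Attending week 48 happens after randomization and may depend on the arm. MI-b adds telephone counseling in response to reported non-adherence, which could plausibly keep poorer adherers in that arm. If people with low levels tend to leave, the arm that loses more of them shows a higher mean among those who remain, even when adherence is the same in both arms.

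Objective 2a, with its stratified repeat in 2c, is the only between-arm comparison in the main objectives that treats drug level as continuous. The week 12 part is the least necessary loss: those levels exist, but are set aside because of what happened later.

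Attendance also does not fully define who can be analysed. Someone may attend both visits off drug and have no level, and such people probably have the lowest exposure.

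**Working it through.** **The plan's own figure.** The documents state no power or sample size for 2a. The only stated power is 77% for the primary endpoint (33% versus 49%, 150 per arm). With a continuity correction and two-sided 0.05: (0.16 − 1/150 − 1.96 × 0.0568)/0.0560 = 0.75, which gives 77.3%. Fisher's exact test gives 78.1%. The figure reproduces, and nothing below depends on it.

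**Inputs**

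- 150 per arm (Randomization and Stratification).
- SD 350 fmol/punch (sub-study I sample size) and SD 694 (Preliminary Data). Both refer to people with perfect adherence; the SD in a mixed cohort is not given.
- A difference of 230 fmol/punch, equated with one tablet per week (sub-study I margin).
- Assumed, because the documents give nothing: retention by arm, and the correlation ρ between drug level and staying.

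**Levels left out of 2a.** Assume that dropouts do not return and that every attendee gives a level.

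- Retention 90/85/80/75% at weeks 12/24/36/48: 300 × 3.30 = 990 levels collected and 2 × 0.75 × 300 = 450 used, so 55% are unused. Of the week 12 levels, (0.90 − 0.75)/0.90 = 17% are unused.
- Retention 80/70/60/50%: 780 collected and 300 used, so 62% are unused. Of the week 12 levels, 38% are unused.

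**Bias with no true effect.** Under a normal selection model with a fraction r retained, the mean among those retained shifts by ρ × SD × m(r), where m(r) = φ(z_r)/r and z_r is the r-quantile of the standard normal.

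- m(0.70) = 0.3477/0.70 = 0.4967; m(0.80) = 0.2800/0.80 = 0.3500; difference 0.1468.
- ρ = 0.5, SD 350: 0.5 × 350 × 0.1468 = 25.7.
- ρ = 0.5, SD 694: 0.5 × 694 × 0.1468 = 50.9.
- Low end (ρ = 0.3, SD 350, retention 70% versus 75%): 0.3 × 350 × (0.4967 − 0.4237) = 7.7.
- High end (ρ = 0.7, SD 694, retention 65% versus 80%): 0.7 × 694 × (0.5698 − 0.3500) = 106.8.
- Equal retention and equal selection: the difference is 0 and the type I error is 5.0%.

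The spurious advantage goes to the worse-retained arm.

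**Scale.** At 70% versus 80% retention, 105 and 120 people remain. For SD 350, SE = 350 × √(1/105 + 1/120) = 46.8, so 25.7 is 0.55 SE and the type I error is about 8.5%. The ratio is the same for SD 694. Over ρ = 0.2 to 0.6 the type I error is 5.6% to 10.1%. The difference detectable with 80% power is 2.80 × SE, about 131 (SD 350) or 260 (SD 694), so the shift is about one fifth of it. Against 230 it is 11% (25.7/230) to 22% (50.9/230).

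**What a model on all levels recovers.** Let a and b be the correlations of staying with the week 12 and week 48 levels, and c the correlation between the two levels. Suppose that everyone has a week 12 level.

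- If staying depends only on the week 12 level, b = ac. With a = 0.5, the both-visits bias is 25.7 or 50.9 at week 12. At week 48 it is c times that: 12.8 to 18.0 (SD 350) or 25.5 to 35.6 (SD 694) for c = 0.5 to 0.7. A likelihood-based model removes both.
- If staying also depends on the week 48 level, the model's remaining shift in each arm is SD × m(b − βa), with β = (c − abk)/(1 − a²k) and k = m(m + z_r). For a = b = 0.5 and c = 0.5, β is 0.427 (70% retained) and 0.442 (80%). The remaining difference is 0.0445 × SD against 0.0734 × SD, or 61%. For c = 0.7 it is 0.0267 × SD, or 36%.

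So the model removes the week 12 bias, but only part of the week 48 bias when staying also depends on the later level.

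**The case against.** The strongest reply is that 2a is an openly declared completer view, one of several looks at the same drug levels. The mITT rule applies in general rather than without exception, and objective 3b is likewise confined to people retained. Objective 4 will show whether attendance differed by arm. The protocol calls its statistics section brief and gives precedence to a fuller SAP, so the t-test or rank-sum line is generic and not a model chosen for 2a. Every non-zero bias above needs a retention gap that the documents do not supply.

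Much of this stands, and it limits the point:

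- A reader might infer that the drug levels are thrown away. The documents do not support that. Week 12 levels of later dropouts enter the primary and key secondary endpoints, and 2d uses all attended visits, though only against cut-offs.
- A reader might infer that the main result is biased. The primary endpoint, as the Primary Endpoints section defines it, keeps everyone dispensed PrEP.
- A reader might infer that 2a favours MI-b. In this model, better retention under MI-b would bias 2a against MI-b.
- A mixed model is not a full cure. Participants with at least one level are also a set formed after randomization, and levels missing because the drug was stopped are unlikely to be missing at random.

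What does not stand is leaving 2a as it is. The objective itself fixes the population, so a later SAP has to change it deliberately. Reporting retention by arm reveals a problem but does not correct it.

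**Conclusion.** The point holds as a recommended improvement to a secondary objective. Objective 2a rests on a subset formed after randomization, departs without explanation from the plan's general mITT principle, and omits collected levels from the only continuous drug-level comparison between the arms.

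The bias is possible, not established. Under the illustrated assumptions it is about 26 to 51 fmol/punch, with a range of about 8 to 107 over the assumptions tried, and zero when retention and selection are equal. These sizes rest on assumed retention and correlations, a normal selection model, and SDs taken from perfect adherers; they scale in proportion to the SD. No stated power figure and no primary or safety conclusion depends on 2a.

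**What to change.** In the SAP, and in the wording of objective 2a:

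- Make the main analysis a repeated-measures linear mixed model on all available DBS TFV-DP levels at weeks 12, 24, 36 and 48, transformed if skewed, in mITT participants with at least one level. Include arm, visit, arm-by-visit and the stratification factors (site, sex assigned at birth, prior PrEP use).
- Report the arm contrasts at weeks 12 and 48, so that the stated time points are kept. Apply the same approach to the stratified repeat in 2c.
- Keep the both-visits comparison as a sensitivity analysis.
- State how visits off study drug, which yield no DBS, are handled in the analysis.
- Add a missing-not-at-random sensitivity analysis, for example with off-drug or post-dropout levels set low or delta-adjusted.

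The cost is SAP wording, one model and the sensitivity runs; no new data are needed. The downside is that the main model assumes missing at random given the observed levels. Off-drug missingness may violate that, which is why the last two items belong with the model.
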